4.16.3 Spectral-Domain Optical Coherence Tomography

Observed value, change from baseline, and percent change from baseline for Foveal Subfield Thickness, Total Macular Volume, Central Horizontal Ellipsoid Width, Central Ellipsoid Area, the square root of the Central Ellipsoid Area and Choroidal Thickness at Foveal Center will be summarised by visit, by eye, and by period.

Presence of Vitreomacular Traction (VMT), Epiretinal Membrane (ERM), Macular Hole (MH), Intraretinal Hyper-Reflective Spots, Cystoid Macular Edema, Subretinal Fluid (SRF), Subretinal Hyper-Reflective Material and Pigment Epithelial Detachment will be summarised by visit, by eye, and by period. Shift from baseline will be evaluated for each of these assessments.

The categories for the shift from baseline for VMT, ERM, MH and Intraretinal Hyper-Reflective Spots assessments are defined as follow:

- Absent at Baseline to Absent
- Absent at Baseline to Present
- Present at Baseline to Absent

- Present at Baseline to Present

The categories for the shift from baseline for Cystoid Macular Edema, SRF, Subretinal Hyper-Reflective Material and Pigment Epithelial Detachment assessments are defined as follows:

- None at Baseline to None
- None at Baseline to Yes, foveal/Yes, non-foveal
- Yes, foveal/Yes, non-foveal at Baseline to None
- Yes, foveal/Yes, non-foveal at Baseline to Yes, foveal/Yes, non-foveal

For VMT, ERM, MH and Intraretinal Hyper-Reflective Spots, ‘Presence’ will be assigned as the ‘worst case’ value. For Cystoid Macular Edema, SRF, Subretinal Hyper-Reflective Material and Pigment Epithelial Detachment, ‘Yes, foveal/Yes, non-foveal’ will be assigned as the ‘worst case’ value.

Image quality will be listed only. This includes the Image Completeness, Centration, Tilt, Motion Artifacts and Signal Strength.

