 - who, in the clinical opinion of the Patient Eligibility Review Committee or Investigator, is not an appropriate candidate for sub-retinal surgery (see the Patient Eligibility Review Plan)
5. Have participated in another research study involving an investigational product in the past 12 weeks or received a gene/cell-based therapy at any time previously, except if treated within in an antecedent study with AAV2-REP1.

Test Product, Dosage, and Mode of Administration: For each eye, subjects will undergo vitrectomy and retinal detachment and receive a sub-retinal injection of up to 0.1 mL of study drug containing 1×10^{11} AAV2-REP1 genome particles (gp).

Reference Therapy (Comparator), Dosage, and Mode of Administration: Not Applicable.

Criteria for Evaluation:

Safety: The safety evaluation will be based on BCVA (as measured by the ETDRS chart); full ophthalmic examination (including IOP, slit lamp examination, lens opacity grading and dilated ophthalmoscopy); SD-OCT; fundus AF; fundus photography; microperimetry; AE reporting; vector shedding and immunogenicity; and vital signs.

Efficacy: The efficacy evaluation will be based on BCVA (as measured by the ETDRS chart); fundus AF; SD-OCT and microperimetry.

Statistical Methodology: No formal sample size calculation will be performed.

Continuous variables will be summarised over time using descriptive statistics (i.e., mean, standard deviation, 95% confidence intervals [CI], median, first and third quartiles, fifth and ninety-fifth percentiles, minimum, and maximum). Categorical variables will be described over time using counts, percentages, and 95% CIs. Summaries will be tabulated by visit and eye. No formal statistical testing will be performed.

AEs will be summarised by system organ class, preferred term, and eye. The number of eyes with an AE, as well as the number of events, will be summarised, by period and eye. Similar summaries will be produced for study drug/procedure-related AEs, AEs leading to discontinuation, and serious AEs. AEs will also be summarised by maximum severity, relationship to study drug/procedure, and time to onset and resolution. Vector shedding and immune response profiles will be described.

The remaining safety evaluations will be analysed using descriptive statistics.

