4.17.3 Slit Lamp Examination

The number and percentage of subjects within each category of Slit Lamp Examinations outcomes will be summarised by visit, by eye, by period as well as overall. Shift from baseline will also be evaluated.

The categories for the shift from baseline for ‘Cornea’, ‘Conjunctiva’, ‘Iris’, ‘Lens’ and ‘Anterior Segment’ assessments are defined as follows:

- Normal/Clinically insignificant abnormality at Baseline to Normal/Clinically insignificant abnormality
- Normal/Clinically insignificant abnormality at Baseline to Clinically significant abnormality
- Clinically significant abnormality at Baseline to Normal/Clinically insignificant abnormality
- Clinically significant abnormality at Baseline to Clinically significant abnormality

The categories for the shift from baseline for ‘Anterior chamber, hypopyon’, ‘Grading of anterior chamber cells’, ‘Grading of anterior chamber flare’ and ‘Vitreous inflammation quantification’ assessments are defined as follows:

- Absent at Baseline to absent
- Absent at Baseline to present
- Present at Baseline to absent
- Present at Baseline to present

For ‘Grading of anterior chamber cells’ assessment, absent is defined as ‘0 Cells’ and present is defined as any other category (except missing).

For 'Grading of anterior chamber flare' assessment, absent is defined as 'Complete absence' and present is defined as any other category (except missing).

For 'Vitreous inflammation quantification' assessment, absent is defined as '0' and present is defined as any other category (except missing).

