4.17.4 Lens Opacity Grades

The number and percentage of subjects within each category of Nuclear Opalescence Grade, Nuclear Colour Grade, Cortical Cataract Grade and Posterior Cataract Grade will be summarised by visit, by eye, by period as well as overall. Shift from baseline will also be evaluated.

The categories for Lens Opacity Grades are defined as Category 1, 2, 3 and 4. Category 1 includes values 1, 1.0 and 0.x. Category 2 includes values 2, 2.0 and 1.x. Category 3 includes values 3, 3.0 and 2.x. Category 4 includes values 4, 4.0, 3.x and any values above 4.

The categories for the shift from baseline are defined as follows:

- No change in category
- Decrease in category
- Category 1 at Baseline to Category 2, 3 or 4
- Category 2 at Baseline to Category 3 or 4
- Category 3 at Baseline to Category 4

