4.17.8 Fundus Photography

Presence and severity of Retinal Pigment Epithelium (RPE) Hyperplasia, Retinal Arteriolar Narrowing, Retinal Vessel Sheathing, Optic Atrophy/Pallor and Optic Disc Swelling will be summarised by visit, by eye, and by period. Shift from baseline will also be evaluated.

The categories for the shift from baseline are defined as follows:

- Absent at Baseline to absent
- Absent at Baseline to present
- Present at Baseline to absent
- Present at Baseline to present

where Absent corresponds to None and Present to Mild, Moderate or Severe.

Image quality will be listed only. This includes image completeness, focus/clarity, field definition, stereopsis, exposure and contrast.

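### SAP 4.16.3 pools foveal with non-foveal OCT findings, so its tables cannot show movement into the fovea or separate new foveal from new non-foveal findings

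*SAP*

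**What the plan says.** SAP 4.16.3 introduces the coding with "The categories for the shift from baseline for Cystoid Macular Edema, SRF, Subretinal Hyper-Reflective Material and Pigment Epithelial Detachment assessments are defined as follows". Four categories follow, with foveal and non-foveal written together as one positive level. The last category is "Yes, foveal/Yes, non-foveal at Baseline to Yes, foveal/Yes, non-foveal". The section then names this pooled level as the worst-case value for all four findings. Its by-visit categorical summary is of presence, without mention of location. SAP 4.17.6 refers back to 4.16.3, so the same tables serve the safety analysis.

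SAP 4.16.2 handles a similar question differently. For autofluorescence lesions it separates subfoveal from not subfoveal, cross-tabulates the two against baseline, and makes subfoveal the worst case.

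Two other sections also reduce graded scales for the shift table:

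- SAP 4.17.3, for anterior chamber cells, flare and vitreous inflammation: "present is defined as any other category (except missing".
- SAP 4.17.8, for fundus photographs: "where Absent corresponds to None and Present to Mild, Moderate or Severe".

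Under SAP 4.3, the Period 2 baseline of the first-treated eye (SE1) is its last value before the second eye's surgery, and so comes after SE1's own surgery. Protocol 13.7.2 asks for OCT shifts from baseline but sets no categories. SAP 4.20, which lists changes from the protocol, does not discuss the pooling.

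**The concern.** Safety is the study's only objective (Protocol 6.1). The surgery detaches the retina, and the injection takes in the fovea where possible (Protocol 9.4). Macular oedema and persistent detachment are named surgical risks, and loss of acuity is an identified risk of the product (Protocol 5.4). Protocol 11.9 lists foveal change among the things SD-OCT is meant to assess. A reader of the safety tables will therefore ask whether fluid or oedema reached the fovea, and in how many eyes. The planned categorical tables cannot answer.

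Two kinds of information are lost:

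- In an eye free of the finding at baseline, a new foveal finding looks the same as a new non-foveal one. This loss does not depend on how common the findings are at baseline.
- In an eye that already has a non-foveal finding, extension to the fovea cannot be told from stability or improvement.

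The second loss bears most on SE1 in Period 2. Whether the first eye worsens after the second dose is a central question in a bilateral study, and SE1 then starts from a post-operative baseline. Protocol 9.8 provides for second-eye surgery before Study Day 21, so that baseline can lie within three weeks of SE1's own procedure. The supportive remapping of SE1 data to its Period 1 baseline is described in SAP 4.16.1 for visual acuity, not for OCT.

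**Working it through.** There is no planned figure to reproduce. The study is descriptive, and the Protocol synopsis says "No formal sample size calculation will be performed". The check is an enumeration of baseline-to-visit transitions, mapped onto the SAP's shift cells.

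**OCT (SAP 4.16.3).** The SAP's labels give three levels, taken in the order none < non-foveal < foveal. Transitions: 3 × 3 = 9. Worsening transitions: 3 × 2 / 2 = 3.

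| Planned cell | Transitions it holds | Worse | Same | Better |
|---|---|---|---|---|
| None to none | none→none | 0 | 1 | 0 |
| None to yes | none→non-foveal, none→foveal | 2 | 0 | 0 |
| Yes to none | non-foveal→none, foveal→none | 0 | 0 | 2 |
| Yes to yes | non-foveal→foveal, two unchanged, foveal→non-foveal | 1 | 2 | 1 |
| Total | 9 | 3 | 3 | 3 |

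So 1 of the 3 worsening transitions is hidden in a mixed cell. The other 2 can be seen as worsening but not told apart. With separate levels there are 9 cells and all 3 worsening transitions are visible.

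**Fundus photographs (SAP 4.17.8).** Four levels: none, mild, moderate, severe. Transitions: 4 × 4 = 16. Worsening: 4 × 3 / 2 = 6. The present-to-present cell holds 3 × 3 = 9 transitions: 3 worse (mild to moderate, mild to severe, moderate to severe), 3 unchanged and 3 better. So 3 of 6 worsening transitions are hidden.

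**Inflammation grades (SAP 4.17.3).** The structure is the same. Any rise from a non-zero baseline grade falls in present-to-present, and any rise from zero is shown as absent to present.

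**Do the by-visit counts recover this?** For slit lamp and fundus, in part: "The number and percentage of subjects within each category of Slit Lamp Examinations outcomes will be summarised by visit", and fundus severity is also summarised by visit. These counts do not follow an eye. If one eye goes from mild to moderate and another from moderate to mild, the counts at the two visits are identical. For OCT location, no by-visit count is specified at all.

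**The case against.** The strongest reply is that little is lost. Two of the three OCT worsening transitions remain visible as new onset. SAP 4.16.3 also summarises change in foveal subfield thickness and total macular volume. Acuity losses of at least 5, 10 and 15 letters are tabulated by eye and period (SAP 4.17.1), and a macula shift to clinically significant abnormality is tabulated under dilated ophthalmoscopy (SAP 4.17.5). Signs of inflammation and other post-operative sequelae in SE1 should be resolved before Period 2 (Protocol 7.1), and a history of inflammatory disorder is excluded at entry (Protocol 8.2). The protocol sets no OCT categories, so nothing departs from it.

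Much of this stands. It makes the inflammation part secondary, since most baselines should be grade zero. It does not remove the OCT point. Thickness and volume are group summaries of a continuous measure and do not say which eyes moved to foveal fluid or oedema. Acuity and ophthalmoscopy do not report its location. Resolution of sequelae is left to the investigator's judgement, and Protocol 10.2 speaks only of significant signs of inflammation. Source listings will exist, but a listing is not a summary.

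A reader might infer more than the documents support:

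- **That worsening is tabulated as no change.** The OCT, inflammation and fundus cells are labelled yes-to-yes or present-to-present. They mix worsening with stability and improvement but do not claim stability.
- **That every worsening by grade goes uncounted.** Slit lamp categories and fundus severity are counted by visit, and onset from none is shown as a shift.
- **That the lens tables share the fault.** SAP 4.17.4 counts all 6 upward moves between its four categories. The top one is open-ended ("Category 4 includes values 4, 4.0, 3.x and any values above 4"), so a rise within it is not counted, but that does not call for a new rule here. Adding a lens-worsening row that leaves out eyes after cataract extraction would drop the eyes whose cataract progressed far enough to need surgery, and would bias the count downward.

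**Conclusion.** The point holds for the four OCT findings. As planned, the categorical tables hide 1 of 3 worsening transitions and cannot separate new foveal from new non-foveal findings. The worst-case value ranks the two equally, although the same SAP ranks subfoveal worst for autofluorescence. This is a loss of detail in a descriptive safety analysis, partly mitigated by the continuous OCT measures. It is neither an error nor a departure from the protocol.

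The conclusion rests on two assumptions. First, the two positive answers are recorded separately, as the SAP's labels indicate; the reading-centre form is not in the documents. Second, foveal involvement is the more important of the two. The documents do not say so outright for these findings, but the autofluorescence ranking and the interest in foveal change in Protocol 11.9 point that way. No baseline prevalence is given, so no number of affected eyes can be stated. The same pooling of inflammation grades and fundus severity is real but of lesser weight.

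**What to change.** In SAP 4.16.3, for the four findings:

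- replace the four-category shift by a 3x3 shift (none, non-foveal, foveal);
- make foveal the worst-case value, in line with 4.16.2;
- summarise the three categories by visit, eye and period.

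As a secondary addition, give the shift tables for anterior chamber cells, flare and vitreous inflammation (4.17.3) and for fundus severity (4.17.8) three rows: increase of at least one grade, no change, decrease. Leave the lens opacity shift as it is.

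The cost is SAP wording and programming. Each OCT shift gains 9 − 4 = 5 cells, or 4 × 5 = 20 over the four findings at each visit, eye and period. No new data or visits are needed if location and grade are held as the SAP's labels imply. A check of the reading-centre data specification would confirm this. The protocol need not change, because 13.7.2 leaves the categories open.

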4.16.4 Macular Integrity Assessment Microperimetry

Mean Sensitivity, Bivariate Contour Ellipse Area 63%, Bivariate Contour Ellipse Area 95% and Fixation Losses will also be summarised by visit, by eye, by period as well as overall. The corresponding 95% CIs will be calculated (See [Section 4.2](#)).

The number and percentage of subjects within each category of Fixation Stability will be summarised by visit, by eye, by period and by surgery window as well as all surgery windows combined. Shift from baseline will also be evaluated.

The categories for the shift from baseline for ‘Fixation Stability’ assessment are defined as follows:

- Stable at Baseline to Stable
- Stable at Baseline to Relatively Unstable/Unstable
- Relatively Unstable/Unstable at Baseline to Stable
- Relatively Unstable/Unstable at Baseline to Relatively Unstable/Unstable

Where microperimetry data are collected using the automated text files, the following algorithm will be used to define the value of Fixation Stability.

- If $P1 \geq 75\%$, then fixation stability is considered as stable.
- If $P1 < 75\%$ and $P2 \geq 75\%$, then fixation stability is considered as relatively unstable.
- If $P1 < 75\%$ and $P2 < 75\%$, then fixation stability is considered as unstable

Image quality will be listed only. This includes image completeness, focus/clarity and field definition.

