13.7.4 Micropertimetry

Fixation Location and Stability, and their shift from baseline, will be summarised by eye, period and visit. Bivariate Contour Ellipse Area and Mean Sensitivity, and their change from baseline, will be summarised by eye, period and visit. An analysis specific to the Sensitivity Points will be performed, the details of which will be described in the GEMINI SAP. Any additional categorical/continuous efficacy endpoints will be summarised using descriptive statistics, with 95% 2-sided CIs calculated where appropriate. Shift from baseline will be summarised by eye and by visit, where applicable.

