2.2.2 Secondary Efficacy Endpoints

- Change from Baseline in BCVA as measured by the ETDRS chart
- Change from Baseline in autofluorescence
- Change from Baseline in SD-OCT
- Change from Baseline in microperimetry

[figure not shown]
3 Study Design

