4.16.1 Visual Acuity

Best-corrected visual acuity (BCVA) and change from baseline will be summarised by visit, by eye, by period as well as overall. The corresponding 95% CIs will be calculated (See [Section 4.2](#)).

Furthermore, the proportion of eyes with a ≥ 10 letters increase, a ≥ 15 letters increase, and an increase or a loss < 5 letters (i.e. change from baseline > -5 letters) will be summarised by visit, by eye, by period as well as overall. The corresponding 95% CI will be presented (See [Section 4.2](#)).

The above main analyses will use the observed case method only. Imputation using LOCF method regardless of the reasons of missing data will be performed for supportive analyses (See [Section 4.8](#)).

In addition to the by-period, by-eye presentation mentioned above, as supportive analyses, for both continuous and categorical endpoints, the period 2 Study Eye 1 data will be presented by

remapping them to visits after their last visit in period 1 and calculating change from baseline using baseline at period 1 for the same eye (Study Eye 1). This way a full picture of Study Eye 1 treatment journey during the entire study will be presented.

For all assessments of periods 1 and 2 of Study Eye 1, the data records will be assigned to calculated visit window (using study day) as described in [Table 2](#) below. The window of the visits following baseline (including unscheduled visits) will be constructed in such a way that the upper limit of the interval falls half way between the two visits.

If a patient has more than one assessment included within a window, the assessment closest to the target day will be used. In case of ties between observations located on different sides of the target date, the value with the later date will be used.

Table 2 **Visit Assignment Windows**

Day / Month	Target Day	Day Range included in the visit
Baseline	0	The last assessment on or before day 0
Day 1	1	Day 1
Day 3	3	Day 2 to 5
Day 7	7	Day 6 to 10
Day 14	14	Day 11 to 22
Month 1	30	Day 23 to 61
Month 3	91	Day 62 to 136
Month 6	182	Day 137 to 272
Month 9	273	Day 228 to 318
Month 12	365	Day 319 to 410
Month 15	456	Day 411 to 501
Month 18	548	Day 502 to 593
Month 21	639	Day 594 to 684
Month 24	731	Day 685 onwards

Both continuous and categorical endpoints for BCVA will be summarised by subgroups mentioned in [Section 4.7](#).

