4.16.2 Fundus Autofluorescence

Observed value, change from baseline, and percent change from baseline for Total Area of Preserved AF, square root of the Total Area of Preserved AF and Distance from Foveal Center (FC) to nearest Border of Preserved AF will be summarised by visit, by eye, and by period.

The number and percentage of subjects with Subfoveal or non-Subfoveal Lesion in Relation to FC will be summarised by visit, by eye, and by period.

Shift from baseline in Lesion will be summarised by calculating the number of subjects falling in each of the following categories:

- Not subfoveal at Baseline to Not subfoveal
- Not subfoveal at Baseline to Subfoveal
- Subfoveal at Baseline to Not subfoveal
- Subfoveal at Baseline to Subfoveal

Those summaries will be presented by visit, by eye and by period.

For Subfoveal or non-Subfoveal Lesion in Relation to FC, 'Subfoveal' will be assigned as the 'worst case' value.

Image quality will be listed only. This includes image completeness, focus/clarity, field definition, exposure, contrast and 'Is the total area of preserved AF fully captured within frame'.

Note: The variable 'Distance from FC to nearest Border of Preserved AF' takes a positive value when 'Location of Lesion in Relation to FC' is Not Subfoveal and a negative value when 'Location of Lesion in Relation to FC' is Subfoveal.

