4.20 Changes in Planned Analyses from the Protocol

There are some changes to the planned analyses described in the protocol.

1. The protocol refers to the assessment of Fixation Location. Because of a change in the way microperimetry data are collected, fixation location is not available in the database. Therefore, Fixation Location was removed from the SAP.
2. The protocol mentions that specific analyses of the sensitivity points (microperimetry) will be performed. These analyses are not included in the SAP as they are considered as exploratory across the BIIB111 program and will be performed as post-hoc analyses, if needed to be consistent with other studies in the same program.
3. For consistency of other studies in the program, time to resolution of AEs will not be summarized.
3. The protocol specifies that LOCF will be used as imputation method for efficacy analyses. The main analyses of categorical and continuous efficacy endpoints will use the observed case method, as the main purpose of the study is the evaluation of BCVA from a safety perspective. Additional supportive analyses of BCVA-related endpoints, including LOCF imputation, will be applied and are described in detail in [Section 4.16.1](#).

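### SAP 4.16.4 does not specify change from baseline for Mean Sensitivity or BCEA, although the protocol requires it and the secondary endpoint is a change

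*SAP*

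**What the plan says.** Protocol 13.7.4 plans the continuous measures as levels and changes: "Bivariate Contour Ellipse Area and Mean Sensitivity, and their change from baseline, will be summarised by eye, period and visit". SAP 2.2.2 carries the endpoint over as "Change from Baseline in microperimetry", and SAP 2.2.1 also lists microperimetry as a safety measure.

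The analysis text in SAP 4.16.4 reads: "Mean Sensitivity, Bivariate Contour Ellipse Area 63%, Bivariate Contour Ellipse Area 95% and Fixation Losses will also be summarised by visit, by eye". It continues with period and overall, and refers to SAP 4.2 for the 95% CIs. It names no change from baseline. The one comparison with baseline in that section concerns the categorical Fixation Stability: "Shift from baseline will also be evaluated". SAP 4.17.9, the safety section for microperimetry, only points back to 4.16.4.

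SAP 4.20 opens with "There are some changes to the planned analyses described in the protocol". Its list covers fixation location, the sensitivity-point analysis, time to resolution of adverse events, and LOCF. Change from baseline in Mean Sensitivity or BCEA is not on it.

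**The concern.** The endpoint is a change, and the section that should produce it plans summaries by visit only. A programmer who follows 4.16.4 literally would tabulate levels, and the listed endpoint would have neither a specified estimate nor a CI. The safety side would not repair this, because it refers back to the same section.

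In many trials a reader could recover the mean change by subtracting two visit means. Here that is unsafe in Period 1. Subjects leave the Period 1 schedule when the second eye is treated (SAP 3.3), the main analysis uses observed cases (SAP 4.8), and the outcome and visual function of the first eye inform when Period 2 starts (SAP 3.1). A later visit mean therefore describes a selected part of the baseline group.

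Mean Sensitivity also carries more weight than before. It is the only retinal-sensitivity measure still planned in 4.16.4, since SAP 4.20 defers the sensitivity-point analysis to post hoc work, if needed.

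**Working it through.** The documents give no numerical target on this point, so there is no plan figure to reproduce. The check has three parts.

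**1. The texts side by side**

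| Measure | Protocol 13.7.4 | SAP 4.16.4 | Departure declared in SAP 4.20? |
|---|---|---|---|
| Mean Sensitivity | value and change | summary by visit, change not named | no |
| BCEA | value and change | 63% and 95%, summary by visit, change not named | no |
| Fixation Stability | value and shift | value and shift | none needed |
| Fixation Location | value and shift | absent | yes |
| Sensitivity points | analysis to be set out in the SAP | absent | yes |
| Fixation Losses | not mentioned | summary by visit | change never planned |

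Elsewhere the SAP names the change where it wants one:
- BCVA (4.16.1): "Best-corrected visual acuity (BCVA) and change from baseline will be summarised by visit, by eye, by period as well as overall".
- Autofluorescence (4.16.2): "Observed value, change from baseline, and percent change from baseline for Total Area of Preserved AF", among other measures.
- SD-OCT (4.16.3): "Observed value, change from baseline, and percent change from baseline for Foveal Subfield Thickness", among other measures.
- Intraocular pressure (4.17.2) and vital signs (4.17.13) also name it.

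A version mismatch does not explain the gap. The SAP is based on protocol version 4 of 30 Oct 2019, and the version 3.0 summary of changes already shows change from baseline in the text of 13.7.4.

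**2. Who contributes to the Period 1 means**

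Inputs:
- about 60 subjects (SAP 3.6);
- about 20 in each of the short, medium and long windows (SAP 3.1);
- six subjects with Period 2 data only (SAP 4.3).

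Assume no dropout, and that a subject contributes to a Period 1 visit only if the window reaches it. Month 6 is then medium + long, and Month 12 is long only.

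| Assumption | Baseline | Month 6 | Month 12 | Month 12 / baseline |
|---|---|---|---|---|
| All 60 have Period 1 data | 60 | 40 | 20 | 20/60 = 33% |
| Six excluded, spread evenly over windows | 54 | 36 | 18 | 18/54 = 33% |
| Six excluded, all in the long window | 54 | 34 | 14 | 14/54 = 26% |

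Let long-window subjects differ from the rest at baseline by d, and let no eye change. The baseline mean is then (mean of the rest) + d × n_long/n_base, and the Month 12 mean is (mean of the rest) + d. The apparent change is d × (1 − n_long/n_base).

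| Assumed d | 20 of 60 | 14 of 54 |
|---|---|---|
| 1 dB | 0.67 dB | 0.74 dB |
| 2 dB | 1.33 dB | 1.48 dB |
| 3 dB | 2.00 dB | 2.22 dB |

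For example, 2 × (1 − 20/60) = 1.33 and 2 × (1 − 14/54) = 1.48. The documents give no value for d, so this is an illustration only.

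**3. The CI of the mean change, in either period**

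By the t formula in SAP 4.21, the half-width for a visit mean is t × SD/√n. With equal SD at both visits and within-eye correlation ρ, the half-width for the mean change is t × SD × √(2(1 − ρ))/√n. At n = 20, t/√n = 0.468, so:
- visit mean: 0.47 SD;
- mean change: 0.47 SD if ρ = 0.5, 0.30 SD if ρ = 0.8, 0.21 SD if ρ = 0.9.

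The result depends on ρ, which cannot be read from summaries by visit. The values of ρ are assumptions. The CI of the change therefore has to be tabulated directly, also in Period 2.

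**The case against.** The strongest reply is that the SAP does not drop the change. It keeps the endpoint in 2.2.2. SAP 4.2 promises summary statistics for all endpoints and gives a CI method for a mean change, and 4.16.4 refers to that section for its CIs. SAP 4.3 defines change from baseline by eye and period without excluding microperimetry. SAP 4.20 declares two other microperimetry departures but not this one, which looks more like a slip than a decision.

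Much of this stands. A reader might infer that the sponsor has decided not to produce the change, and the documents do not support that. What they support is that the change is not specified for these variables. General definitions say how to compute a change, but not that this section reports one, and sections 4.16.1 to 4.16.3 do say so.

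Other readings that go too far:
- **That visit means compare different subjects throughout the study.** In Period 2 all treated subjects are scheduled to Month 12, so the mix changes only through dropout or missed tests. In Period 1 the later visits hold a shrinking subset of the same subjects. Levels show change there, but not cleanly.
- **That a planned change in Fixation Losses was removed.** The protocol never planned one, because the SAP added that measure.
- **That the Month 12 count is firm.** Subjects whose second eye is not treated stay in Period 1 (Protocol 8.3 and 10.2). The ±14-day window, and the advice to align second surgery with a planned visit (Protocol 10.1), could let some medium-window subjects contribute.

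The study is also descriptive, with no formal testing, and no decision rule uses this endpoint. The values are collected, so the change can be tabulated at any time. That limits the harm but does not make the specification complete.

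**Conclusion.** The point holds as a mismatch between endpoint and analysis. For Mean Sensitivity and both BCEA measures, the SAP section does not specify the change that the protocol requires and the SAP's own endpoint list names, and the departure is not declared. It should be corrected before the analysis.

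The size differs by period. In Period 1, about two thirds to three quarters of the baseline subjects are absent from the Month 12 mean (67% to 74%), and the rest are not a random sample. This assumes the planned 20/20/20 windows, no dropout, and no one staying in Period 1 because the second eye is untreated. In Period 2 there is no built-in change of mix, and the loss is the missing estimate and CI of the mean change. The dB figures are conditional on an assumed baseline difference and are not a prediction.

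**What to change.** Amend the first sentence of SAP 4.16.4 so that it plans:
- observed value **and change from baseline** for Mean Sensitivity, BCEA 63% and BCEA 95%;
- observed value for Fixation Losses (change is optional);
- each per visit, eye and period **and overall**, with n and 95% CIs.

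The overall summary is already planned and should be kept. If the omission is intended, the alternative is to declare and justify it in SAP 4.20.

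Show n at every visit. Change from baseline makes each eye its own control and removes the artefact from the baseline mix. It does not bring back subjects who have moved to Period 2, nor remove selection on the outcome of the first eye. A Period 1 Month 12 mean change still describes the subjects who remain.

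The cost is one sentence and a few table rows. Microperimetry is already scheduled at screening, at the Period 2 baseline and at Months 1, 3, 6 and 12 (Protocol Table 1).
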